The primary hypothesis is that children in TEAM-ED will have more symptom-free days at 3, 6, 9, and 12-months compared to eUC. Previous asthma interventions have demonstrated that improvements of 0.85-0.95 SFD/2 weeks are feasible and clinically meaningful.^{59,60} Based on our prior data, we estimate a pooled standard deviation (SD) of SFD to be 3.5 and within-subject correlation (ICC) of 0.3. We calculated power for the intervention effect on SFD while justifying repeated assessments for outcomes (3, 6, 9, 12 months).^{61,62} A sample size of 182 subjects per group will provide >90% power to detect a difference of 0.85 in SFD at a 2-sided 5% significance level.⁶³ We also calculated the smallest detectable differences in secondary outcomes with 80% power based on prior data.

We also aim to test whether children in TEAM-ED will have fewer unscheduled asthma visits over 12 months compared to eUC. Based on our preliminary data and data for similar populations, we estimate the baseline unscheduled asthma visit rate ranges 0.7-1.5 per person year. A sample size of 365 subjects will provide 80% power to detect a rate ratio of 0.7 if the control group has rate of 0.7 per person year. For preventive measures such as preventive medication use, in our prior study, 59% of children used a preventive medication at baseline. With 182 subjects in each group, we will have 90% power to detect an increase of 16% in using a two-sided Z test at a significance of 5%.

Primary Analysis:

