The primary analyses will be performed according to the intention-to-treat principle and will include all randomized subjects. Substantial attention will be invested in participant retention; reasons for any subject withdrawals that may occur will be carefully documented. Missing data patterns will be examined by comparing subjects who discontinued with those who remained in the study. Inference based on the proposed methods GEE and/or LMM is valid provided that missing data follows the missing completely at random (MCAR) assumption. However, if the occurrence of missing data depends on the observed response but is independent of unobserved data (MAR), weight GEE (WGEE) will be used. Sensitivity analysis to the MAR assumption will also be carried out by modeling the between-group difference using WGEE.^{67,68} Separate secondary per protocol analyses will be performed, however, results of these analyses are potentially subject to bias and will be interpreted with appropriate caution.

Cost Effectiveness Analysis: *Establish the financial sustainability of the intervention with a specific focus on ultimate dissemination.* We will assess the health and economic benefits of TEAM-ED from both the societal and the Medicaid perspectives. We also will use Diffusion of Innovations Theory to help understand how this innovative model can be maintained in the current system of care.

We will use cost-effectiveness (CE) methodology^{69,70} to assess the health and economic benefits of TEAM-ED versus eUC over 12 months. The basecase analysis will be conducted from the societal perspective which includes all identifiable costs and benefits, regardless of whom they impact. Since the majority of subjects are eligible for Medicaid (73% based on prior work⁵⁹), a second analysis will take the Medicaid perspective. The intervention benefits will be assessed using the primary outcome (mean symptom-free days over 12 mos.).^{71,72}

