We will consider the total cost of initiating and maintaining the program as well as the incremental cost-effectiveness ratio (ICER) of TEAM-ED versus eUC. The ICER is the difference in cost between the 2 study groups relative to the difference in the number of symptom-free days (SFD) gained between the 2 groups. The main outcome for the analysis from the societal perspective will be the ICER, defined as: $(\Delta Medical + \Delta Productivity + \$Program) / \Delta SFD$, where $\Delta = (TEAM-ED) - (eUC)$. We will bootstrap⁷⁴ the ICER to estimate standard error and to evaluate the uncertainty around the point estimate. The ICER will be compared to similar estimates from the literature.^{71,72} An acceptability curve, linking various values of 1 SFD to the probability of TEAM-ED being cost-effective, will be plotted.⁷⁵ The study from the Medicaid perspective will use the cost-benefit approach to economic evaluation. Benefits will be described as the net difference in medical and productivity costs between children in the TEAM-ED and eUC groups and accounts for a potential reduction in unplanned visits as well as an increase in number of preventive visits. The cost is equivalent to the cost of the program ($Net Monetary Benefit = \Delta Medical - \$Program$).

COVID-19

In response to the COVID-19 crisis, we will follow the Human Subjects Research guidelines outlined by the University of Rochester to continue enrollment for this study. Please find the following link for these guidelines: <https://www.urmc.rochester.edu/coronavirus/coronavirus-research/guidance-for-researchers/human-subjects-research.aspx>. We will minimize in-person contacts to only those tasks necessary to conduct the research (e.g., obtaining consent, collecting breathing measurements if needed). We will ensure that team members are appropriately trained in safety measures, maintain social distancing when possible, use personal protective equipment for themselves and research subjects (and family members), and will ensure proper cleaning/sanitizing of hands, equipment and workstations. We will continue to monitor and follow the updated guidelines put forth by the UofR in the link above.

We've included a brief, optional survey to assess how the COVID-19 Crisis is affecting children with asthma and their families. We will ask the caregivers if they would be willing to answer these questions at the end of follow-up surveys that we are already conducting.

References

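### The planned bootstrap standard error for the ICER has no stable value when the symptom-free-day difference is near zero; report net benefit instead

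*Combined protocol and SAP*

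**What the plan says.** The passages are in the Analysis section of the combined protocol and SAP, under Cost Effectiveness Analysis and Sample Size.

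- Definition: "The ICER is the difference in cost between the 2 study groups relative to the difference in the number of symptom-free days (SFD) gained". The numerator adds the medical, productivity and programme components.
- Role: "The main outcome for the analysis from the societal perspective will be the ICER". It is also to be compared with published estimates.
- Uncertainty: the plan will bootstrap "the ICER to estimate standard error and to evaluate the uncertainty around the point estimate". It names no interval type, no number of resamples and no rule for resamples in which the SFD difference is zero, negative or very small.
- Further output: "An acceptability curve, linking various values of 1 SFD to the probability of TEAM-ED being cost-effective, will be plotted".
- Benefit measure: the primary outcome, described as "mean symptom-free days over 12 mos".
- Planning values, under Sample Size: "we estimate a pooled standard deviation (SD) of SFD to be 3.5 and within-subject correlation (ICC) of 0.3", four follow-up assessments, 182 children per group, and more than 90% power for a difference of 0.85 SFD.

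**The concern.** A standard error describes a ratio well only when the denominator stays clear of zero. If the denominator's sampling distribution has appreciable density around zero, the ratio has no finite variance in the normal approximation. A bootstrap will still print a number, but that number depends on which few resamples happened to land closest to zero.

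The sign is a second difficulty. A negative ICER arises both when the intervention is cheaper and better and when it is dearer and worse. A standard error computed across such values pools opposite conclusions.

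The standard error is the only numerical uncertainty statistic the plan names for its main societal outcome. A reader would take it as the error bar when comparing the ICER with the literature.

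**Working it through.** **1. Reproduce the plan's power.** Inputs from Sample Size: SD 3.5, within-subject correlation 0.3, four assessments, 182 per group, difference 0.85, two-sided 5%.

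- SD of a child's four-assessment average: 3.5 × √((1 + 3 × 0.3)/4) = 2.412.
- SE of the group difference: 2.412 × √(2/182) = 0.253 SFD per 2 weeks.
- Planned effect over SE: 0.85/0.253 = 3.36.
- Power: 91.9%, which agrees with the stated figure of more than 90%. A single time point would give only 63.9%, so the averaged difference is what the plan used.

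**2. How often does the denominator reach zero?** Under a normal approximation, the share of resamples with a non-positive SFD difference is Φ(−observed difference/SE). No cost figure is needed. The last column assumes 2,000 resamples, since the plan gives no number.

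| Observed difference (SFD per 2 weeks) | Difference/SE | Share ≤ 0 | Expected count in 2,000 |
|---|---|---|---|
| 0.85 | 3.36 | 0.04% | about 1 |
| 0.50 | 1.98 | 2.4% | 48 |
| 0.425 | 1.68 | 4.6% | 93 |
| 0.25 | 0.99 | 16% | about 320 |

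If the true effect is 0.85, the observed difference still falls below 1.96 SE (1.96 × 0.253 = 0.496) with probability Φ(1.96 − 3.36) = 8%. If the true effect is smaller, this happens more often.

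**3. Effect on the ICER standard error, simple simulation.** The documents give no costs, so these are assumptions: cost difference USD 300 with SE USD 150, independent of SFD. Scaling to a year gives an SFD standard error of 0.253 × 365/14 = 6.6. Fifty runs of 2,000 draws gave:

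- at 0.85 (ICER USD 13.5 per SFD): standard error from USD 10 to 618, median 15;
- at 0.50 (USD 23): USD 93 to 22,480;
- at 0.42 (USD 27): USD 201 to 11,994.

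**4. Same check by resampling children, over a range of costs.** Assumptions: 182 children per arm, right-skewed costs, cost difference USD 300, correlation parameter −0.2 between SFD and cost, SFD scaled by 26. There were 2,000 resamples and 20 reruns on one fixed data set. The SE of USD 150 in step 3 corresponds to a patient-level SD of 150/√(2/182) = USD 1,431, which lies inside the range used here.

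| Cost SD (USD) | ICER SE at 0.85, min / median / max | at 0.50 | at 0.25 | Net-benefit SE, every effect size |
|---|---|---|---|---|
| 1,000 | 10 / 16 / 728 | 109 / 396 / 1,616 | 513 / 3,800 / 38,253 | 175–186 |
| 2,000 | 15 / 21 / 1,024 | 118 / 436 / 2,202 | 634 / 4,337 / 46,436 | 256–275 |
| 4,000 | 26 / 34 / 1,615 | 151 / 542 / 3,374 | 925 / 5,290 / 62,806 | 445–476 |

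Net benefit is valued at an assumed USD 20 per SFD. At cost SD 2,000, the acceptability-curve probability at that value moved between reruns only within 0.69–0.72 (at 0.85), 0.43–0.46 (at 0.50) and 0.25–0.28 (at 0.25).

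**5. Intervals for the ratio.** At cost SD 2,000 and an observed 0.85, the 95% percentile limits were fairly stable across reruns: lower −5.7 to −3.3, upper 45 to 55. At 0.25 they were not usable: lower −681 to −327, upper 426 to 894. The 95% Fieller set is bounded only if the difference exceeds 1.96 SE. That holds at 0.85 (3.36 SE) and fails at 0.425 (1.68 SE).

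**The case against.** The strongest reply is that the plan does not rest on the standard error alone. The same paragraph commits to an acceptability curve, which stays well defined whatever the sign of the SFD difference and was stable in the checks above. The bootstrap is also meant to evaluate uncertainty more generally, and the cited bootstrap reference covers confidence intervals by its title. At the design effect, percentile limits from the same resamples are usable. All of this stands. A reader might infer that the whole cost-effectiveness uncertainty assessment would be invalid, and the documents do not support that.

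It does not rescue the standard error. Wording that leaves room for percentile limits does not specify them, and nothing says what happens when the denominator is near zero. The net monetary benefit defined for the Medicaid perspective contains no SFD term, so it is not a net-benefit version of the ICER.

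Two other stronger readings should be set aside.

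- Because Sample Size speaks of "improvements of 0.85-0.95 SFD/2 weeks are feasible and clinically meaningful", a reader might infer that annual costs would be divided by a 2-week SFD difference. That phrase describes earlier interventions. The economic section sets a 12-month comparison and refers to the number of symptom-free days gained, which reads naturally as a 12-month count. One clarifying phrase is enough.
- A reader might also infer that costs and SFD would be resampled separately. The plan does not say so.

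**Conclusion.** The plan is wrong as written on one statistic of the economic analysis. The ICER standard error is unreliable at any observed SFD difference of about 0.5 per 2 weeks or less. Even at the planned 0.85 it can be dominated by a single resample: at cost SD 2,000 the median was USD 21 but the maximum was USD 1,024. Between reruns it varied more than tenfold at every effect size tabulated.

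The crossing shares rest on the plan's own SD, correlation, number of assessments and group size, plus a normal approximation. The dollar figures rest on assumed costs, but the pattern held across a fourfold range of cost SD. The acceptability curve, the primary SFD analysis, the sample size and the safety monitoring are not affected. The point is worth correcting because the ICER is the main societal outcome.

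**What to change.** Amend the Cost Effectiveness Analysis text as follows.

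1. Remove the standard error of the ICER as a reported quantity.
2. From the same bootstrap samples, report incremental net benefit (value per SFD × SFD difference − cost difference) with a confidence interval over a stated range of values per SFD, the cost-effectiveness plane, and the acceptability curve already planned.
3. Report the ICER as a point estimate. Give a percentile or Fieller interval only when the SFD difference is clearly away from zero, and state that the 95% Fieller set is unbounded when the difference is below 1.96 SE.
4. As a clarification, say that the SFD denominator is a 12-month total and how the follow-up reports are scaled to it.

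The cost is a few sentences in the SAP. No new data or further resampling are needed.

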There may be some cost to participate in this study. Participants in the TEAM- ED group will be responsible to purchase medications and spacers that may be prescribed by the telemedicine provider as well as any fees associated with telemedicine visits (e.g., co-pays etc.) completed through the study (these are medical processes that should occur according to the national guidelines regardless of the child's participation in the study). Based on our prior work with this population, we anticipate that most of the children will have some form of health insurance to cover the cost of visits and the medications with minimal or no co-pay fee. In our prior studies we found that approximately 70% of families in the City of Rochester were insured with Medicaid which often eliminates co-pay fees for medications and care. If a child does not have insurance, the study team will help the family secure health insurance. If a child is unable to obtain health insurance or if a family or provider expresses a financial concern, the study team will pay for the participant's asthma medication and spacer prescribed by the telemedicine provider. If there is no insurance reimbursement for the telemedicine visit, subjects will not be asked to pay any additional costs (e.g., co-pay). Participants and their insurance company will be responsible for the cost of all standard of care office visits and additional medications prescribed by their PCP.

- **Data Storage and Confidentiality**

To maintain the integrity, security, and confidentiality of study data, the data will be maintained in a secure and encrypted web-based database and/or a password protected database on a secure university network drive. The majority of data will be entered through REDCap™, a secure password-protected website supported by the University of Rochester. Subject tracking information will also be entered into a secure password-protected database created with Microsoft Access, that is only accessible on a secure university network drive and research personnel must use their University NetID and password to access the databases. No subject data will be stored on the internal hard drives of any computers. After data validation and analysis, subject information will be de-identified. All consent forms, paper surveys and additional correspondence will be stored in a locked filing cabinet in a locked hallway or locked office, and will only be accessible by the study staff.

- **Safety**

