Three main categories of costs to be considered include programmatic costs, productivity costs, and medical costs estimated at the individual child level. Programmatic costs include costs of initiating and running the program, hiring and training staff, purchasing or leasing equipment, staff travel, and information system costs. Programmatic costs will be tracked by the UR General Pediatric Division Administrator and the UR Telemedicine Program Administrator. Research-related costs that are not associated with the intervention and would not exist beyond the duration of the study will not be

included. Per person programmatic costs will be calculated by dividing the total costs of the program by the total number of children with persistent asthma in the EDs. We will determine productivity costs based on the amount of time parents take from work to care for sick children or take them to a doctor. Time from work will be valued at the median of the Bureau of Labor Statistics pay scale estimates based on age, race and gender. We will assess the impact of the intervention on medical costs using both parent-reported health care utilization data and medical record review. We will ask parents at each follow-up about their child's visits to the ED, urgent care facility, or primary care office, as well as hospitalizations. Health care use will be converted to costs using the NYS Medicaid fee schedule and other sources. Money spent out-of-pocket by caregivers to cover the cost of medical procedures, medications, or equipment will also be included in the medical costs. Annual medical costs per person will be analyzed using a 2-part model to adjust for zero expenses in a given year.⁷³ All costs will be adjusted to the last year of the intervention using the appropriate component of the Consumer Price Index (CPI).

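### The Medicaid net-benefit formula counts a medical saving as a loss, and it disagrees with the plan's own benefit sentence on productivity costs

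*Combined protocol and SAP*

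**What the plan says.** All the relevant text is in the combined protocol and SAP, Analysis section, under Cost Effectiveness Analysis. The base case is societal, and "a second analysis will take the Medicaid perspective".

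- **Societal ICER.** The numerator is "\Delta Medical + \Delta Productivity + \$Program" and the denominator is the difference in symptom-free days. The same sentence defines Delta as TEAM-ED minus eUC. No other definition of Delta appears in the document.
- **Medicaid analysis, in words.** Later in the same paragraph the plan adopts a cost-benefit approach: "Benefits will be described as the net difference in medical and productivity costs between children in the TEAM-ED and eUC groups". It adds that this "accounts for a potential reduction in unplanned visits as well as an increase in number of preventive visits".
- **Medicaid analysis, formula.** The next sentence begins "The cost is equivalent to the cost of the program ($Net Monetary Benefit" and gives the expression "Net Monetary Benefit = \Delta Medical - \$Program". Delta is not redefined. The backslashes and dollar signs are typesetting marks and play no part in this point.

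**The concern.** One symbol is used with two opposite signs. In the ICER, Delta Medical is added to program cost, so it is an incremental cost and a saving makes it negative. In the Medicaid formula, program cost is subtracted from Delta Medical, which makes sense only if a saving is positive. An analyst who computes Delta Medical once and uses it in both places will report a net loss for a program that saves more than it costs.

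Separately, the words and the formula do not describe the same quantity. The benefit sentence includes productivity costs and the formula has no term for them. Two analysts, each following part of the plan, would report different net benefits.

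Financial sustainability is one of the listed study objectives, and the Medicaid perspective was chosen because most of the children are expected to be eligible for Medicaid. If sign and cost content are settled only after the data are seen, the payer conclusion depends on a choice made with the results in view.

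**Working it through.** The documents give no cost figure and no net-benefit figure, so there is nothing to reproduce. The check is substitution of the plan's own definition.

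**Inputs.** Delta = TEAM-ED minus eUC; ICER numerator = Delta Medical + Delta Productivity + Program; Net Monetary Benefit (NMB) = Delta Medical - Program. All come from the Cost Effectiveness Analysis. Let P be program cost per child and S the medical saving per child with TEAM-ED, so Delta Medical = -S. A negative S is a cost increase.

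**Sign.**

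- As written: NMB = -S - P = -(S + P).
- Savings minus program cost: NMB = S - P.
- Gap: (S - P) - (-S - P) = 2S.
- The two have opposite signs when (-S - P)(S - P) = P² - S² is below zero, that is, when the absolute value of S exceeds P. This covers savings and increases alike.
- With Delta Productivity at zero, the ICER numerator is P - S. That is the exact negative of S - P, so a correctly signed NMB and the ICER numerator must agree on whether the program saves money.

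In units of P, over an assumed range of S:

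| Medical saving S | NMB as written | NMB = S - P | ICER numerator (Delta Productivity = 0) |
|---|---|---|---|
| 0.5P | -1.5P | -0.5P | +0.5P |
| P | -2P | 0 | 0 |
| 2P | -3P | +1P | -1P |
| 3P | -4P | +2P | -2P |
| -2P (increase) | +1P | -3P | +3P |

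In the 2P row the ICER numerator shows a net saving of 1P while the written NMB shows a loss of 3P. In the last row the program raises medical costs by twice its own cost, and the written NMB shows a gain of 1P. In the 0.5P row both versions are negative, so only the size is wrong.

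An example with assumed amounts: program 100 dollars, medical cost 700 dollars under TEAM-ED and 1,000 under eUC. As written, NMB = (700 - 1,000) - 100 = -400. With savings positive, NMB = (1,000 - 700) - 100 = +200.

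**Productivity.** With the sign put right:

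- Formula (medical costs only): NMB = -(Delta Medical) - P.
- Sentence (medical and productivity costs): NMB = -(Delta Medical) - (Delta Productivity) - P.
- Difference: -(Delta Productivity), which is exactly the productivity saving.

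With assumed P = 300 dollars and S = 200 dollars, medical costs alone give 200 - 300 = -100. Adding an assumed productivity saving of 50, 100 or 200 dollars gives -50, 0 or +100. Which text is followed can therefore decide whether the program appears to pay for itself.

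**The case against.** The strongest reply is that the intent is plain. Delta is defined in a clause attached to the ICER. The Medicaid text then moves to a cost-benefit framework, says what the benefit is, and identifies the cost as program cost. Net benefit is benefit minus cost, so the first term must be meant as a saving, and a careful analyst would read it that way.

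The inference about intent is fair and probably right. It does not repair the formula. The benefit sentence speaks of a difference between the groups without giving the direction of subtraction, so it does not redefine Delta. To reach the intended result, the analyst has to set aside the only written definition.

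On productivity, it can be said that the sentence tells the analyst what to describe and the formula what to calculate, so both could be honored by describing both components and computing one. That reading is possible. But the sentence defines the benefit, and the formula is benefit minus cost. The natural reading is that the same benefit enters both, and the plan should say so if it does not.

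It is also true that no stated figure is miscalculated, and that every dollar amount above is assumed. The identity 2S and the sign condition need none of them.

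A reader might go on to infer two further errors, which the documents do not establish:

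- **Diluted program cost.** The plan divides total program cost by the number of children with persistent asthma in the EDs, which could look like spreading an in-trial cost over too many children. That needs assumptions about both numerator and denominator. The objective stresses dissemination, and the plan excludes research costs that would end with the study. Both support a roll-out reading in which total and divisor describe the same population and nothing is diluted.
- **Out-of-pocket spending.** The plan says "Money spent out-of-pocket by caregivers to cover the cost of medical procedures, medications, or equipment will also be included in the medical costs", and caregivers' spending is not a Medicaid cost. But that sentence lists costs for the economic evaluation as a whole and does not fix a Medicaid cost set. The Compensation section also expects most children to have insurance to "cover the cost of visits and the medications with minimal or no co-pay fee", so any effect is likely small.

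**Conclusion.** The formula is wrong as written. Under the plan's only definition of Delta, the Medicaid Net Monetary Benefit differs from savings minus program cost by twice the medical saving, and it has the wrong sign whenever the absolute medical cost difference exceeds program cost. A program that lowers medical costs can never show a positive net benefit, while one that raises them by more than its own cost does. This rests on the text alone, given only that program cost is positive.

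The mismatch over productivity costs is also real, and its size is exactly the productivity difference between the groups. The documents do not allow that difference to be estimated.

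A reader might infer that the whole economic evaluation, or the trial's main result, is compromised. It is not. The societal ICER uses Delta Medical with the correct sign. The symptom-free-day analysis and the sample size do not use this formula. The defect is confined to the second economic analysis.

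**What to change.** In the Cost Effectiveness Analysis, replace the Medicaid formula with: Net Monetary Benefit = (eUC medical cost - TEAM-ED medical cost) - Program. Equivalently, leave Delta as defined and write -(Delta Medical) - Program.

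Then make the benefit sentence and the formula agree on productivity costs. Leaving them out of both fits a Medicaid payer perspective, since the plan measures productivity as parents' time away from work, and they remain in the societal ICER. If they are meant to count, the formula needs the term and the plan should say why a Medicaid analysis includes it.

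The cost is one formula line and one sentence. No data collection, sample size or other analysis changes. The correction should be made before costs are compared by group.
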